2. PROTECTIONS AGAINST RISK

Lifestyle interventions that are personalized to individual functional capacity and activity tolerance have been well-established to be safe for older cancer survivors. As a research group, we have the experience and expertise to ensure the safety of participants and minimize aforementioned risk. There will be an educational session for the registered dietitian and exercise scientist on the unique needs and challenges of older cancer survivors prior to the intervention. The content will be taught by members of the research team, gerontologist ([name]), registered dietitian ([name]), and an exercise scientist ([name]), will host a comprehensive training session for the registered dietitian and exercise scientist about the unique needs, goals, and contextual factors of older cancer survivors. This training will detail their duties within this intervention including: discussing the core educational elements (provided within the study binders), ensuring the appropriateness of the registered dietitians and exercise scientist's guidance and counseling, recommendations, informing them of potential reported barriers to improving dietary quality and resistance training, encourage tailored messaging for older cancer survivors, recording process data (e.g., number of visits, adherence to protocol) within the REDCap platform, accessing the REDCap-based exercise/dietary logs of the intervention participants, and ensuring the safety of participants. In addition, [name] and [name], will be the primary contacts for the registered dietitian and exercise scientist, respectively, if any concerns arise about the safety of participants. The registered dietitian and exercise scientist will also be encouraged to communicate any challenges or difficulties to the PI and/or during the regular meetings with the study team.

As in similar prior lifestyle intervention trials conducted by the study team members, we will obtain a release form from each participant's primary care physician for involvement in the study. We will ask the primary care physicians to complete a form related to the inclusion and exclusion health conditions—yes/no. If an activity-related injury or illness does occur, the PI ([name]), the co-I ([name]), who is an exercise scientist, and study member ([name]), who is a senior oncologist, will be consulted according to the type of symptom reported. In some instances, it may be appropriate to reduce the participant's resistance training goals. If the injury or symptoms do not resolve after an appropriate period of time, the participant will be referred to her primary care provider for further evaluation. The participant will be encouraged to follow the primary care provider's instructions.

After the baseline assessment, participants will be provided (on paper and via email) a weblink to access their REDCap-based weekly logs. The research assistant will provide a demonstration on how to access the REDCap-based logs and enter their weekly dietary intake and exercise adherence. Intervention participants will be advised to contact the research assistant in the event of technical difficulties. Weekly REDCap-based logs of the intervention participant's dietary intake and exercise adherence will offer the registered dietitian and exercise scientist as well as study team insight into their goal progression. These logs will provide an additional method to monitor potential participant difficulties, which the study team will address, therefore, reducing participant risk.

All study members are trained in methods to reduce risks. All study materials and information will be kept on the OSU Medical Centers' secure computer network that is behind a firewall and password-protected. Specifically, the data will be housed within The Center for Biostatistics at OSU. At the dissemination phase, the data will be shared and housed within OSUWMC Information Technology Department, Biomedical Informatics program, an extensive research-oriented virtual server and storage area network facility. The Biomedical Informatics program also aligns with and leverages the enterprise support model offered by OSUWMC IT including a support desk and a dedicated security and risk assessment team. Any transfer of the data will be behind an internal, password-protected firewall. All applications and processes that use patient information are governed by HIPAA in the course of daily operations. The study will follow all existing procedures for protecting confidentiality and anonymity.

3. BENEFITS

For the older cancer survivors participating the intervention, they may receive benefit from their participation in terms of improving their physical function (primary study outcome), learning new resistance training techniques, trying new healthy foods and recipes, deepening their personal health and nutrition knowledge, and improving their physical and mental health outcomes. Participation may result in increased knowledge of personal health risks, ways to improve physical function, how to be active safely and effectively as an older cancer survivor, how to overcome barriers to improve dietary quality and resistance training, and increased self-efficacy to work toward their health goals. This knowledge can motivate them to continue these healthy behaviors to support their life as an older adult with a history of cancer. Participants may also gain a better understanding of technology used in this study including Zoom®, FaceTime®, and REDCap. In addition, participants may feel a sense of rapport and support with the registered dietitian and exercise scientist. The participants, registered dietitian, and exercise scientist may experience pride in knowing that they are contributing to research to improve the health and well-being of cancer survivors. The low level of risk associated with this study is overshadowed by the potential benefits. We believe that the aforementioned risks of this study are minimal and reasonable, when compared to: 1) the scientific knowledge to be gained by performing these studies and; 2) the potential benefits to study subjects.

For others outside this research study, results from this study will provide vital information about improving physical function and associated health outcomes among OCS. It will significantly contribute to the understanding of retention, adherence, and efficacy of diet and resistance training interventions among OCS as well as older adults. This study also will provide information about the acceptability and feasibility of technology-based intervention among older cancer survivors, a population who are often excluded from technology-based interventions. Thus, the multiple anticipated benefits to the subjects and others outweigh the minimal risks for participants.

4. STUDY TERMINATION PROCEDURES

Participants will be informed that they can stop participating at any time with no penalties to them. If participants decide to stop being in the study, their surveys will be deleted from the REDCap system. However, if participants only choose to answer certain questions without explicitly stating a desire to no longer participate, survey data for those answered questions will be stored.

V. STATISTICAL METHODS

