2. HOW IT WILL BE DONE

The E-PROOF intervention core content is from publicly available, pre-existing educational content provided by the NIA, NCI, American Cancer Society, American College of Sports Medicine (ACSM), and OSUCCC. The dietary core content includes: 1) recommended amount and sources of protein intake; 2) healthy eating as an OCS; 3) protein intake benefits; and 4) importance of maintaining physical function through diet. The resistance training intervention core content includes: 1) recommended frequency and resistance training exercises; 2) resistance training benefits; 3) different muscle groups; and 4) the importance of maintaining physical function through resistance training. Intervention participants will also have the option of attending Zoom®-based social hours (held at 7-8pm EST, 1 day/week, weeks 3, 6, 9) to share their thoughts and experiences with each other. Informed design was used for intervention development by reviewing relevant evidence; replicating prior successful intervention elements from the PI and co-Is and; incorporating feedback from the Cancer and Aging Research Group's patient advocacy group (see Letter of Support).

Randomization and Baseline Assessment: Subjects will be block randomized by the number of physical function limitations measured by the PFSS.⁴⁰ At the in-person visits at baseline and end-of-study, study staff will measure the physical function (SPPB), muscle strength (handgrip, SPPB), height, weight, and waist circumference of all participants (intervention and control). The Research Electronic Data Capture (REDCap) secure platform^{41,42} will be used for baseline questionnaire data collection, which will assess dietary quality (DHQIII), self-reported exercise, HRQoL, self-efficacy, and demographic and clinical information. After data collection, the research assistant will show intervention participants how to access the REDCap-based logs and enter their weekly dietary intake and exercise adherence. At the end of the baseline visit, intervention participants will receive a binder with printed educational materials on increasing dietary protein, healthy eating, and resistance training to preserve or rebuild lean body mass as a reference tool. Resistance bands (three levels of Thera-bands®), and resistance band exercise guidelines (exercises by muscle group, proper form, how to rate difficulty) will be distributed to intervention participants.

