5. HOW THE DATA WILL BE COLLECTED OR ACCESSED

Research materials will come from the following sources: Total Cancer Care registry data from the study site, and the Cancer Supportive Care Clinic, part of OSUCCC will be used for recruitment purposes. . Participants' physical function (as measured by the SPPB), muscle strength (handgrip, SPPB), weight, height, and waist circumference will be collected at the in-person meetings (baseline and after the 12-week intervention). Online Research Electronic Data Capture (REDCap)-based questionnaires at baseline and end-of-study will collect assessing dietary quality (DHQIII), self-reported exercise (frequency/duration/intensity), health-related quality of life (RAND-36), and self-efficacy. Basic demographic (e.g., age, race, education) and health characteristics (e.g., comorbidities, stage of cancer at diagnosis, treatments received) will be collected through REDCap questionnaires. These questionnaires will be self-administered and a research assistant will be available to address any technological difficulties. Three months after the 12-week intervention, all participants will return for an in-person assessment of physical function (SPPB), muscle strength (handgrip, SPPB), and health-related quality of life (via REDCap questionnaire).

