7. HOW THE DATA ARE STORED AND PROTECTED

The proposed intervention utilizes an individualized approach and does not operate in group settings, therefore ensuring participants' privacy. Confidentiality will be protected in several ways. All data points will be collated and stored on a REDCap database, a secure web application. Data will be used only in aggregate and no identifying characteristics of individuals will be published or presented. Confidentiality of data will be maintained by using research identification numbers that uniquely identify each individual. Safeguards will be established to ensure the security and privacy of participants' study records. The information collected from participants in this study has a low potential for abuse, since the data do not address sensitive issues. Nevertheless, appropriate measures will be taken to prevent unauthorized use of study information. All computer systems will be password-protected against intrusion. All network-based communications of confidential information will be encrypted. Data other than demographic information do not use names as an identifier. The research number will be used.

All paper files and computer files with the de-identified data will be stored under lock and key at all times. The files matching participants' names and demographic information with research numbers will be kept in a separate room and will be stored in a locked file that uses a different key from that of all other files. Only study personnel will have access to these files, and they will be asked to sign a document that they agree to maintain the confidentiality of the information. After the study is completed, local data will be stored with other completed research studies in a secured storage vault.

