2. DATA ANALYSIS PLAN

Aim 1: The feasibility of implementing a 12-week online diet and resistance training intervention with OCS will be determined by the study accrual rate, retention rate, and adherence rate. The study accrual rate will be calculated by dividing the number of potential participants that passed screening by the total number of participants started in the study after appropriate informed consent procedures. The recruitment goal is set at 70 participants recruited over a 9-month period. Retention rate will be calculated by dividing the total number of participants initiated by total number of participants in the study at baseline and 12 weeks (end-of-study). Retention goal for this trial is 80%. If 80% (56/70) of participants are retained at end-of-study, the retention goal for this trial will be achieved. Previous studies by the study team had similar recruitment and retention rates of older participants.⁷¹⁻⁷³ We are confident in our ability to recruit and retain the study participants necessary to conduct the proposed study. Participants will be determined to be adherent if they attend ≥80% of the intervention sessions (in-person meetings with study staff and online intervention sessions).^{71,74,75} Overall adherence and

retention rates and associated 95% confidence intervals will be reported at baseline, end-of-study, and 3-month follow-up.

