Aim 2: The primary outcome of the SPPB will be assessed at three time points: baseline, end-of-study, and 3-month follow-up. Efficacy will be based on 12 weeks. The SPPB score is a continuous variable, collected as the total score ranging from 0-12. Group differences in SPPB scores over the time will be tested using repeated measures ANOVA (SAS PROC MIXED). Using the planned contrasts command, we will investigate the changes in SPPB scores within each group, and between the intervention and control groups at end-of-study. Descriptive statistics and frequency distributions will be used to characterize the sample. To examine the effect of the intervention on the changes in physical function, a linear mixed effect model will be adopted using SAS PROC MIXED procedure. The intervention group (intervention vs. control) and time points (baseline, end-of-study, 3-month follow-up) serve as the categorical predictors, together with the intervention*time interaction term. A significant intervention*time interaction effect would indicate a differential change pattern over the time between the groups. Using post-hoc contrasts, we will compare group differences in all collected variables at each time point. Using planned contrasts command, we will investigate for each group the change from baseline to end-of-study, from end-of-study to 3-month follow-up, and from baseline to 3-month follow-up to capture the change patterns over the phases and Bonferroni correction will be applied. Preliminary effect sizes will be generated to inform future trials. A Shapiro-Wilk test, skewness, kurtosis, and Q-Q plots will be used to assess normality of survivor baseline and end-of-study outcomes. Based on normality tests, change in participant outcome measures from baseline to end-of-study will be assessed using paired t-tests or Wilcoxon's signed rank tests.⁷⁶ Analysis will be carried out using intent-to-treat (all participants) and modified intent-to-treat (adherent participants only). All quantitative analyses will be performed using SAS version 9.4.

REFERENCES References

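### Deleting the surveys of participants who withdraw conflicts with intent-to-treat on all participants for the questionnaire outcomes

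*Combined protocol and SAP*

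**What the plan says.** Section IV.4 sets the rule for a participant who leaves: "If participants decide to stop being in the study, their surveys will be deleted from the REDCap system". It gives one exception, for people who skip items: "without explicitly stating a desire to no longer participate, survey data for those answered questions will be stored".

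Section 5 (How the Data Will Be Collected or Accessed) lists diet quality, self-reported exercise, RAND-36 HRQoL and self-efficacy as REDCap questionnaires at baseline and end-of-study. HRQoL at the 3-month visit is also a REDCap questionnaire. Demographic and health characteristics "will be collected through REDCap questionnaires" as well.

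The physical measures have a different source. Under Randomization and Baseline Assessment in section III.2, "study staff will measure the physical function (SPPB), muscle strength (handgrip, SPPB), height, weight, and waist circumference of all participants". Section 7 (How the Data Are Stored and Protected) adds: "All data points will be collated and stored on a REDCap database, a secure web application".

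For Aim 2, section V.2 (Data Analysis Plan) says "Analysis will be carried out using intent-to-treat (all participants", alongside a modified version limited to adherent participants. It also says "we will compare group differences in all collected variables at each time point". For Aim 1, the same section sets the retention goal: "If 80% (56/70) of participants are retained at end-of-study, the retention goal for this trial will be achieved".

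**The concern.** Explicit withdrawal happens after randomization. Under the rule in IV.4 it removes data that had already been collected, so the questionnaire dataset becomes restricted to people who did not formally leave. That is not an intent-to-treat set for these outcomes, three of which (dietary quality, HRQoL and self-efficacy) are named in the Aim 2 hypothesis.

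Three things are at stake:

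- **Secondary outcomes.** The mixed model in V.2 could use a leaver's baseline survey and any completed follow-up survey. Deletion prevents this.
- **Week-12 efficacy data.** Efficacy is judged at 12 weeks, but participants are followed for three more months. Someone who completes week 12 and then withdraws loses both the baseline and the week-12 surveys, so a later event changes the efficacy dataset.
- **Feasibility.** Retention is an Aim 1 outcome, and describing who left needs their baseline data. Leavers could still be compared with stayers on baseline SPPB, handgrip, anthropometry and the screening physical function subscale, none of which is named for deletion. They could not be compared on baseline HRQoL, diet, exercise, self-efficacy or questionnaire-reported clinical history.

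**Working it through.** **Step 1: does the rule reach completed surveys?** The deletion sentence in IV.4 refers to the participant's surveys without qualification. The sentence after it is framed as a contrast and stores given answers only where the person has not explicitly asked to stop. That exception would be unnecessary if answers given before withdrawal were kept anyway. The plain reading is therefore that completed surveys are deleted, and no other section says otherwise.

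**Step 2: set the two rules side by side.**

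| Data | Source | After explicit withdrawal | Needed by V.2 |
|---|---|---|---|
| Diet quality, exercise, HRQoL, self-efficacy | REDCap questionnaire | Deleted | Yes, at each time point collected |
| Demographics, health history | REDCap questionnaire | Deleted | Yes, to describe the sample |
| SPPB, handgrip, anthropometry | Staff measurement, stored in REDCap | Not stated | Yes |

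In the first two rows, a participant cannot have the surveys erased and also be in an all-participants analysis. V.2 gives no missing-data method that would address this.

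**Step 3: size at baseline.** Inputs: 70 randomized (section V.1) and a retention goal of 56 of 70 (section V.2).

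- The plan's own figure reproduces: 56/70 = 80%.
- Losses by week 12 with retention exactly at goal: 70 − 56 = 14, and 14/70 = 20%.
- Let f be the share of those losses that are explicit withdrawals. The documents do not give f, so it is taken over its full range from 0 to 1. Baseline survey sets remaining = 70 − 14f.

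| f (assumed) | Baseline sets erased | Baseline sets left |
|---|---|---|
| 0 | 0 | 70 (100%) |
| 0.5 | 7 | 63 (90%) |
| 1 | 14 | 56 (80%) |

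If surveys completed before withdrawal were kept, all 70 baseline sets would remain whatever the value of f.

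**Step 4: size at week 12.** A completed week-12 survey is lost only if the participant withdraws explicitly after completing it. The documents give no number for this. Each such participant removes between 1/70 = 1.4% (full retention) and 1/56 = 1.8% (retention at goal) of the week-12 survey records.

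**The case against.** The strongest reply is that little is lost for the treatment comparison. The main outcome is SPPB, which staff measure, and efficacy is judged at 12 weeks. Someone who leaves before week 12 has no week-12 survey to delete. A baseline-only record adds nothing to the paired tests in V.2 and little to a change contrast in the mixed model. It can also be argued that the intent-to-treat phrase only marks a contrast with the adherent-only set and does not promise complete records, and that deletion may be a deliberate protection promised in consent.

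Much of this stands. Before week 12 the cost falls mainly on the description of leavers, and the primary analysis is not shown to be affected. The 14 is the most the week-12 goal allows, not an expected loss. It is also not a ceiling for the final dataset, because retention could miss the goal and later withdrawals would erase further baseline sets. The consent pages are not in the reviewed text, so what participants were told could not be checked.

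It does not remove the conflict. Ordinary dropout leaves data uncollected, whereas this rule destroys data already in hand, including week-12 outcomes of people who leave during follow-up. A narrower reading of the intent-to-treat phrase still leaves the commitment to compare all collected variables at each time point. Redefining the questionnaire analysis set would make the text consistent, but the data would still be lost.

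**Conclusion.** The concern holds for the questionnaire-based secondary outcomes and for the questionnaire-reported description of the sample. Sections IV.4 and V.2 cannot both be followed for anyone who explicitly withdraws. By week 12, with retention at goal, 0% to 20% of baseline survey sets could be erased. The loss of week-12 surveys is 1.4% to 1.8% of records for each withdrawal after completion, with the number of such withdrawals unknown. These figures rest on the plain reading of the deletion sentence and on an unknown share of explicit withdrawals. No direction of bias can be stated from the documents. The primary SPPB analysis would be affected only if staff-measured records were also removed. The text leaves that open and should settle it. This should be corrected, because deleted surveys cannot be recovered at the analysis stage.

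**What to change.** Replace the deletion sentence in section IV.4 with wording such as:

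> Data collected up to the time of withdrawal, including surveys and staff-measured outcomes, are kept and included in the intent-to-treat analysis. No further data are collected unless the participant agrees. Data are deleted only at the participant's specific request.

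Report the number of deletion requests by arm, and align the consent wording. The reference to staff-measured outcomes also settles whether SPPB, handgrip and anthropometry are kept.

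The cost is one protocol sentence and the matching consent text, through an IRB amendment. If participants have already consented under a promise of deletion, that promise stands for them unless they are re-consented, so the change may apply only to later enrolments.
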